### 5.1.8 Cardiac Monitoring

Minor EKG changes are not uncommon following romidepsin administration. Cardiac assessments must be performed for all study patients. **The Investigator must perform the primary assessment and is responsible for the cardiac safety of the patients (local cardiologist may be consulted, if preferred).**

#### 5.1.8.1

#### Cardiac Alert Findings

In the event of an alert finding, the individual decision about a delay of administration, dose reduction, or withdrawal from the study will be made by the Investigator (in association with local cardiologist, if preferred). All alerts must be confirmed via a manual read of the patients ECG; the machine reading alone is not adequate. The following findings are considered to be cause for alert and if they occur,

should be reported as AEs or SAEs, as appropriate:

- QTc  $\geq$ 500 msec
- Ventricular arrhythmia: VT ( $\geq$ 3 beats in a row) or VF;
- Sinus tachycardia (pulse  $>$ 140/min after recumbency);
- Heart rate  $\geq$  120 bpm with  $\geq$  20 bpm increase from previous evaluation;
- New occurrence of atrial dysrhythmias (SVT, atrial fibrillation, or atrial flutter); or
- Abnormal ST and/or T-wave changes including ST depression of  $\geq$ 2 mm (as measured from isoelectric line to the ST segment at a point 60 msec at the end of the QRS complex); T-wave inversion of  $\geq$ 4 mm (measured from isoelectric line to peak of T-wave) as long as the main QRS vector is positive;
- Ventricular tachycardia, including Torsade de Pointes.

See Table 4 for recommended dose reductions.

#### **5.1.8.2 Electrocardiograms**

Single ECGs (12 lead) should be performed during screening (days -14 to -1) and weekly during cycle 1. Subsequently, ECG will be performed on Day 8 of each cycle to cycle 6, then at the discretion of the Investigator (within 1 hour prior to the romidepsin administration, after administration of antiemetic/premedication).

If the QTc is  $\geq$ 500 msec, ECGs should be repeated 2 more times for a mean of three QTc values. Minor ECG changes are expected following romidepsin administration (refer to current Investigator's Brochure). All abnormalities must be confirmed by the investigator's manual read of the patient ECG (or local cardiologist, if preferred). Abnormal alert findings, based on manual read, should be reported as AEs or SAEs, as appropriate. ECGs must also be performed at the final study visit, whenever clinically indicated and at all visits for follow-up of AEs.

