### 5.1.3

#### Required Blood Parameters and Other Investigations Prior to Each Treatment (Except Cycle 1 Day 1)

Before the start of each treatment, patients should be reassessed and the following criteria must be fulfilled:

- ANC > 1000/dL
- Platelet count  $\geq$  50, 000/dL
- Serum creatinine concentration  $\leq 2.0 \times$  ULN or  $\leq$  baseline, or creatinine clearance  $> 50$  ml/min
- AST (SGOT) and ALT (SGPT)  $\leq 2.0 \times$  ULN or  $\leq 3.0 \times$  ULN in presence of demonstrable liver metastases
- Bilirubin concentration  $\leq 2.0 \times$  ULN
- Serum potassium is  $\geq$  institutional LLN and magnesium is  $\geq$  laboratory LLN (supplements must be given to patients whose potassium is < laboratory LLN and/or whose magnesium is < laboratory LLN and serum electrolytes must be rechecked prior to romidepsin administration).
- Recovery of any drug-related non-hematological toxicity to Grade 1 or less, unless otherwise indicated

- ECG schedule as specified in Section 5.1.8.2.

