- **Nausea/vomiting:** Romidepsin is moderately emetogenic. Ondansteron 8 mg IV will be given prior to Romidepsin injections. Nausea and vomiting should be treated aggressively, with agents such as prochlorperazine, metoclopramide, 5-HT-3 inhibitors, or benzodiazepines. Patients should be strongly encouraged to maintain liberal oral fluid intake during therapy, especially during the initial 14 days of each treatment cycle.
- **Fatigue:** May be cumulative with increasing cycles of therapy. Can be treated as indicated by the treating physician.
- **Anemia:** Treatment with oral 5-azacitidine and romidepsin can cause dose-related anemia. Transfusions or erythropoietin may be utilized as clinically indicated for the treatment of anemia, but should be clearly noted as concurrent medications.
- **Thrombocytopenia:** Treatment with Oral 5-azacitidine and Romidepsin can cause dose-related thrombocytopenia. Transfusion of platelets may be used if clinically indicated. Dose modification for thrombocytopenia is allowed in a manner consistent with the guidelines for dose modification (Section [6.3]). Prophylactic folic acid and vitamin B12 supplements may be necessary to reduce hematologic toxicity.
- **Neutropenia:** Prophylactic use of colony-stimulating factors including G-CSF, pegylated G-CSF or GM-CSF should not be utilized during the first cycle of therapy. These factors may be utilized if clinically indicated in subsequent cycles.
- **Hypokalemia or hypomagnesemia** should be corrected prior to administration of Romidepsin, and consideration should be given to monitoring potassium and magnesium in symptomatic patients (e.g. patients with nausea, vomiting, diarrhea, fluid imbalance or cardiac symptoms.)
- **Oral Mucositis:** Oral 5-azacitidine may cause mucositis (includes stomatitis or mucosal inflammation of gastrointestinal and genitourinary tracts); which may require dosage modification. Prophylactic folic acid and vitamin B12 supplements are necessary to reduce treatment-related mucositis.
- **Hepatotoxicity:** Liver function test abnormalities have been observed with Oral 5-azacitidine use. Persistent abnormalities may indicate hepatotoxicity and may require dosage modification.

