#### **5.1.8.3 All Dosing Days**

- ECGs within 1 hour prior to the administration of romidepsin (after administration of anti-emetic/pre-medication)

In case of the cardiac findings (alerts) above, an individual decision about a delay of administration, dose reduction, or withdrawal from the study will be made by the Investigator who may wish to consult with a local cardiologist.

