### 6.3.1 Romidepsin Dose Modifications

#### Romidepsin dose modification in case of cardiac toxicity

The guidelines for cardiac monitoring and timing of ECG assessments are presented in Table 7. Prolongation of QTc  $\geq 500$  msec is considered to be an alert associated with romidepsin administration

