## **7. ADVERSE EVENTS: LIST AND REPORTING REQUIREMENTS**

### **7.1 Safety Evaluation Procedures**

#### **Adverse Event Reporting**

An adverse event is defined as any unfavorable and unintended change in the structure, function, or chemistry of the body temporally associated with the use of the study drugs, whether or not considered related to the use of the product. Any worsening (i.e., any clinically significant adverse change in frequency and/or intensity) of a preexisting condition that is temporally associated with the use of the study drugs product, is also an adverse event.

Adverse events may occur in the course of receiving study drugs or within the follow-up period specified by the protocol, as well as from overdose (whether accidental or intentional), from abuse, and from withdrawal.

Adverse events will be graded and recorded throughout the study according to NCI-CTCAE, version 4.0. Toxicities will be characterized in terms including duration, intensity, and time to onset. Safety endpoints will include all types of adverse events, in addition to laboratory safety assessments, ECOG performance scale status, ECGs, and vital signs.

The investigator must assess all abnormal laboratory results for their clinical significance. If any abnormal laboratory result is considered clinically significant, the investigator must provide details about the action taken with respect to the test drug and about the patient's outcome.

The following safety evaluations will be performed during patient screening and at defined points during the course of the study:

- Vital signs
- Laboratory studies complete blood count (CBC), serum chemistry, urinalysis, coagulation studies (PT/PTT), pregnancy test, LDH
- Electrocardiograms (ECG)
- Physical examinations
- Performance Status Evaluation using the ECOG scale
- Adverse event monitoring using the NCI CTCAEv4.0

The STUDY FLOW CHART (Section 10) provides specific details on collection time points.

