d) PK for Oral 5-azacitidine /Romidepsin: See figure 1 for details.  
e) To be done within 4 weeks of treatment start date  
f) To be done within 1 week of treatment start date  
g) Not necessary if conducted within 72 hours of screening assessment  
h) PD for Oral 5-azacitidine /Romidepsin: See figure 1 for details.  
i) Sodium, potassium, chloride, calcium, and glucose are part of the electrolyte assessment at every time point. Magnesium and phosphorous will be added to the electrolyte panel at Screening, and repeated before administration of romidepsin.  
j) Follow-up visits will be every 3 months for 1 year, or until the patient begins a new treatment for their disease for any patient that did not progressed on study.  
k) Based on clinical assessment  
l) For CNS disease only. Follow up MRI to be done at the discretion of the treating investigator.

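### The study calendar schedules one on-treatment ECG in cycle 1 (Day 8) where Section 5.1.8.2 requires weekly ECGs, so the Day 15 and Day 22 pre-infusion ECGs are missing; Section 5.1.8.3 leaves the minimum from cycle 2 unclear

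*Combined protocol and SAP*

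**What the plan says.** ECG timing is set in three places.

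- **Section 5.1.8.2, cycle 1:** "Single ECGs (12 lead) should be performed during screening (days -14 to -1) and weekly during cycle 1".
- **Section 5.1.8.2, later cycles:** "Subsequently, ECG will be performed on Day 8 of each cycle to cycle 6, then at the discretion of the Investigator".
- **Section 5.1.8.3**, under a heading that covers all dosing days and gives no cycle limit: "ECGs within 1 hour prior to the administration of romidepsin".
- **Section 10, EKG row:** marks at screening, cycle 1 Day 8, Day 8 of cycles 2 onward, end of treatment and end of study. The romidepsin row of the same table marks Days 8, 15 and 22 in cycle 1 and in cycles 2 onward.

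The cross-references do not agree on which place governs.

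- Section 5.1.3 (checks before each treatment): "ECG schedule as specified in Section 5.1.8.2".
- Section 6.3.1: "The guidelines for cardiac monitoring and timing of ECG assessments are presented in Table 7". Table 7 lists findings and dosing actions but no ECG times.
- Section 7.1: "The STUDY FLOW CHART (Section 10) provides specific details on collection time points".

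**The concern.** The calendar asks for less than the text in cycle 1, and no rule says which prevails. Someone scheduling visits from the calendar, as Section 7.1 invites, would leave out the Day 15 and Day 22 ECGs.

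Table 7 holds and then reduces romidepsin for a QTc of 500 msec or more, T-wave inversion and ST depression. None of these can be seen without an ECG, so under the calendar two of the three cycle 1 infusions have no scheduled tracing that could trigger the hold. The antiemetic adds to the point. Section 5.1.7 states "Ondansteron 8 mg IV will be given prior to Romidepsin injections", and Section 5.1.8.3 times the ECG after the antiemetic, so that tracing is the check on the two drugs together. Section 7.2.2.3 reports one QTc of 534 msec on romidepsin, in a subject who had also received ondansetron. That subject was in a myeloma study combining romidepsin with bortezomib; the event was rated possibly related to romidepsin and unlikely related to bortezomib. Section 2.3.6 lists QT prolongation among the reasons for discontinuation in at least 2% of patients in either CTCL study.

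**Working it through.** The plan gives no figure to reproduce, so the check sets the schedules side by side and counts.

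**Step 1. Required ECGs by source** (on treatment; screening and end visits excluded)

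| Period | 5.1.8.2 | 5.1.8.3, if it sets frequency | Calendar |
|---|---|---|---|
| Cycle 1, before the 3 infusions | 3 | 3 | 1 |
| Cycles 2–6, per cycle | 1 | 3 | 1 |
| Cycles 1–6, pre-infusion total | 3 + 5 = 8 | 6 × 3 = 18 | 1 + 5 = 6 |
| After cycle 6, per cycle | discretion | 3 | 1 |

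The 3 under 5.1.8.2 assumes that the weekly cycle 1 ECGs fall on infusion days. Weekly days in a 35-day cycle are 1, 8, 15, 22 and 29, so Days 8, 15 and 22 are included on any such reading. Counting every weekly ECG, the calendar holds 1 of 3 to 5, depending on whether Days 1 and 29 count. Through cycle 6 the gap between 5.1.8.2 and the calendar is 8 − 6 = 2, all of it in cycle 1.

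**Step 2. Could the Day 8 mark stand for the whole of cycle 1?** Three features of the calendar speak against it.

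- Seven other rows mark cycle 1 Days 8, 15 and 22 separately: concurrent medications, physical exam, vital signs, performance status, CBC, toxicity and romidepsin.
- The EKG row's Day 8 mark for cycles 2 onward matches the Day 8 rule in 5.1.8.2 through cycle 6, so Day 8 appears to mean Day 8.
- Where the chemistry row shows fewer draws than are needed before dosing, footnotes a and i say so (footnote i: "Magnesium and phosphorous will be added to the electrolyte panel at Screening, and repeated before administration of romidepsin"). The EKG row has no such note.

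**Step 3. Number of ECGs absent from the calendar.** Per patient: 3 − 1 = 2. Section 13.2 gives 9 patients in stage 1, 15 more in stage 2 (24 in all), stopping with 2 or fewer responses among the first 9, and 10 patients in the exploratory cohort.

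- Full accrual: (24 + 10) × 2 = 68.
- Phase II stops at stage 1: (9 + 10) × 2 = 38.
- True response rate 25%: P(X ≤ 2 of 9) = 0.601, expected Phase II size 9 + 15 × 0.399 = 15.0 (the plan's own figure is 15), giving (15 + 10) × 2 = 50.
- True response rate 50%: P(X ≤ 2 of 9) = 0.090, expected size 9 + 15 × 0.910 = 22.65, giving (22.65 + 10) × 2 = 65.3, about 65.

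**The case against.** **The calendar mark may not be literal.** In the same grid the optional biopsy has its one on-treatment mark at cycle 1 Day 8, although its window runs from Day 8 to Day 21, and the CT mark sits under Day 8 although scans follow cycles 2 and 6. A merged cell would also appear as one mark followed by blanks. This cannot be fully excluded from the extracted text. But the biopsy and CT marks carry superscripts that qualify them, and the EKG Day 8 marks carry none.

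**The dosing text already governs.** Section 5.1.3 names 5.1.8.2 at the point of dosing, while the pointer in 7.1 is general. The synopsis also places cycle 1 safety evaluations on Days 1, 8, 15 and 22, and Section 7.1 counts ECGs among safety evaluations. All of this is fair, and it makes the weekly rule the likely intent. It also makes the calendar the schedule that is wrong; it does not remove the conflict.

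**The counts overstate the harm.** They would equal missed ECGs only if every site worked from the calendar alone, and the number actually missed could be zero. That stands: they measure what the calendar leaves out.

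**The infusion-day reading is inferred.** The one-hour wording in 5.1.8.2 sits in the sentence on later cycles. This also stands, and the assumption is stated, with support from 5.1.8.3.

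**The QT risk is small.** Section 7.2.2.3 concludes that romidepsin has no significant QT effect, with no QTc above 480 msec and no torsade in the analysed studies. Section 3.2.11 excludes patients with QTc of 500 msec or more and those on drugs that significantly prolong QT, potassium and magnesium are checked before each dose, and clinically indicated ECGs remain required. This limits the severity but does not justify leaving the calendar as it is.

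**Conclusion.** The concern holds. In cycle 1 the calendar omits two pre-infusion ECGs per patient (Days 15 and 22) that 5.1.8.2 requires: 38 to 68 across Phase II and the exploratory cohort. The range assumes that the exploratory cohort fills, that every patient receives all three cycle 1 infusions, and that the weekly ECGs coincide with infusion days. Missed infusions would lower it. The documents give no basis for estimating how many cardiac alerts would go undetected.

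From cycle 2 the point is weaker. Section 5.1.8.2 and the calendar agree on Day 8 through cycle 6, and 5.1.8.3 conflicts with them only if read as a frequency rule. After cycle 6 the calendar keeps Day 8 while 5.1.8.2 leaves ECGs to discretion. The three schedules nest, so a site doing the fullest one meets them all.

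This is a safety-monitoring inconsistency that should be corrected. It does not affect the response rate or the design's error rates.

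**What to change.** 1. In the Section 10 EKG row, mark cycle 1 Days 15 and 22. Add any other weekly cycle 1 ECG that 5.1.8.2 intends: Day 1 is already a calendar visit, Day 29 is not.
2. State whether 5.1.8.3 sets how often ECGs are done or only when they are done relative to the infusion. Align the EKG row from cycle 2 onward with the answer, including after cycle 6. Whether to require an ECG before every infusion from cycle 2 is for the investigators.
3. Point Sections 5.1.3, 6.3.1 and 7.1 to one governing schedule, and remove the statement that Table 7 gives ECG timing.

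The cost is wording. The Day 15 and Day 22 ECGs fall at visits that already include physical exam, vital signs, CBC and infusion, and they add nothing beyond what 5.1.8.2 requires. Two more ECGs per cycle in cycles 2 to 6 would follow only if 5.1.8.3 is confirmed as a frequency rule.

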#### **5.1.8.3 All Dosing Days**

- ECGs within 1 hour prior to the administration of romidepsin (after administration of anti-emetic/pre-medication)

In case of the cardiac findings (alerts) above, an individual decision about a delay of administration, dose reduction, or withdrawal from the study will be made by the Investigator who may wish to consult with a local cardiologist.

## **5.2 Dose-Limiting Toxicity**

A dose limiting toxicity (DLT) is defined as any toxicity not specifically included in section 5.2 that occurs within cycle 1 and is considered at least "possibly related to study drug administration." DLT is also defined as any toxicity possibly related to drug, occurring up to 7 days after completion of cycle 1 that results in a delay of initiating cycle 2. For patients who discontinue study drug administration after Cycle 1, DLT will be defined as any toxicity not specifically included in section 5.2 that occurs within 30 days of the last dose of drug on study, in cycle 1 that is considered at least possibly related to study

drug.

DLTs include:

- Hematologic dose-limiting toxicity will be defined as either Grade 4 neutropenia that does not resolve to  $\leq$  Grade 2 within  $\leq$  7 days, any Grade 4 thrombocytopenia, or any Grade 5 hematologic toxicity. At least three patients in each cohort must be evaluable for hematologic toxicity.
- Non-hematologic dose-limiting toxicity will be defined as any Grade 3, 4 or 5 non-hematologic toxicity, with the specific exception of:
- Grade 3 nausea or Grade 3 vomiting that in the opinion of the investigator occurs in the setting of inadequate compliance with supportive care measures specified in Section 5.1.7 and lasts for less than 48 hours.
- Grade 3 diarrhea that in the opinion of the Investigator occurs in the setting of inadequate compliance with supportive care measures specified in Section 5.1.7 and lasts for less than 48 hours.
- Grade 3 dehydration that, in the opinion of the investigator, occurs in the setting of inadequate compliance with supportive care measures specified in Section 5.1.7 and lasts for less than 48 hours.
- Grade 3 acidosis or alkalosis that responds to medical intervention by returning to  $\leq$  Grade 2 within 48 hours.
- Isolated (i.e. no other abnormalities) Grade 3 elevation of liver function tests (LFTs) without associated clinical symptoms, lasting for  $\leq$  5 days in duration.
- Isolated (i.e. no other abnormalities) Grade 3 elevation of amylase without associated clinical symptoms, lasting  $\leq$  5 days
- Grade 3 hypocalcemia, hypokalemia, hypomagnesemia, hyponatremia, or hypophosphatemia that responds to medical intervention.
- Grade 3 hypercholesterolemia.
- Grade 3 hypertriglyceridemia
- Grade 2 Alopecia
- Grade 3 Constipation
- Grade 3 Fatigue

Management and dose modifications associated with the above adverse events are outlined in Section 6.

### **5.3 General Concomitant Medication and Supportive Care Guidelines**

Because there is a potential for interaction of oral 5-azacitidine and romidepsin with other concomitantly administered drugs through the cytochrome P450 system, the case report form must capture the concurrent use of all other drugs, over-the-counter medications, or alternative therapies. The Principal Investigator should be alerted if the patient is taking any agent known to affect or with the potential to affect selected CYP450 isoenzymes.

Carefully monitor prothrombin time (PT) and International Normalized Ratio (INR) in patients concurrently administered ISTODAX® and Coumadin derivatives

Patients must be instructed not to take any additional medications (including over-the-counter products) during the trial without prior consultation with the PI. All medications taken within 30 days of screening

and medications and supportive therapies that are administered during the study must be recorded in the patient's CRF and in the source documents. Supportive therapy, that is ongoing at baseline, will be permitted during the treatment phase of the study. If other therapy for the disease is required, continuation of the study treatment should be discussed with the lead investigator and sponsor. Concomitant medications for other medical conditions are permitted as clinically indicated subject to specific protocol requirements outlined below.

#### Permitted medications and treatments

- **The prophylactic use of antiemetics is strongly encouraged**, but antiemetics that significantly prolong QTc (e.g., palonosetron) or that significantly inhibit CYP3A4 (e.g., aprepitant) must be avoided (see Appendix 1, and 2, respectively). Granisetron and ondansetron are the antiemetics most commonly utilized in other romidepsin clinical trials.
- Patient's electrolytes (serum potassium and magnesium) must be measured, and must receive supplement infusions to correct any levels outside of those stipulated per protocol. Patients must then undergo a repeat biochemistry test to demonstrate values are within the accepted range before the patient is re-dosed with romidepsin.

#### Prohibited concurrent therapy

- Concomitant use of other anti-cancer therapies, including radiation, thalidomide, or other investigational agents is not permitted while subjects are receiving protocol therapy during the treatment phase of the study.
- Any medications listed in Appendix 1 which may cause QTc prolongation or inducing torsades de pointes should not be used.
- Concomitant use of CYP3A4 inhibitors with romidepsin should be avoided (excluding granisetron and ondansetron) to prevent potential increase in romidepsin exposure during concomitant treatment with these drugs. Should a patient already enrolled on this study require treatment with these drugs (as listed in Appendix 2) romidepsin must be interrupted prior to starting these drugs and should not resume until a washout period of at least 5 half-lives has elapsed.
- Strong CYP3A4 inhibitors may increase concentrations of ISTODAX® and should be avoided.
- Potent CYP3A4 inducers may decrease concentrations of ISTODAX® and should be avoided
- Any medications that have the potential to alter serum electrolytes (e.g., diuretics) should be monitored very closely for electrolyte abnormalities as these can contribute to the risk of QT prolongation and ventricular arrhythmias.

